9.2.2 Urinalysis

Urinalysis test results will be listed. All positive findings in the microscopic examination will be listed.

Observations outside the normal range will be flagged. The abnormal quantitative values will be flagged with 'L' for values below the lower limit of the laboratory's normal range, 'H' for values above the upper limit of the laboratory's normal range, or 'Ab' for abnormal qualitative test results. All original and unscheduled assessments will be listed.

9.3 Vital Signs

The observed data for blood pressure (systolic and diastolic), heart rate (pulse), pulse oximetry, and body temperature will be listed by patient, and time point. Change from baseline values for blood pressure (systolic and diastolic), and heart rate (pulse) will be derived and listed. The overall qualitative assessment for vital signs will be listed.

For systolic and diastolic blood pressure and heart rate, the observed values and change from baseline data will be summarized by group and time point. Table summaries will include descriptive statistics showing the number of observations (n), mean, SD, median, minimum, and maximum value.

Figures of the observed mean response will be used to visualize blood pressure and heart rate response by time point. The two study groups will be shown in the same figure.

PAREXEL International Statistical Analysis Plan

Medivir
Protocol: MIV-711-202

Final 1.0
16 January 2018

9.4 12-Lead Safety ECG

Observed quantitative results for RR, PR, QRS, QT, QTcB (corrected QT according to Bazett), QTcF (corrected QT according to Fridericia) and heart rate will be listed for each patient. Change from baseline for QT, QTcB, QTcF will be derived and listed.

The overall qualitative ECG assessment Abnormal NCS, Abnormal CS, and any comments will be listed for each patient.

For QT, QTcB, QTcF the observed and change from baseline data will be summarized by study group and time point. Summaries will include tables of descriptive statistics showing the number of observations (n), mean, SD, median, minimum, and maximum value.

Figures of the observed mean response will be used to visualize QTcB and QTcF response by time point. The two study groups will be shown in the same figure.

The number and percentage of patients having observed QT, QTcB, QTcF values that satisfy the following conditions will be summarized by time point and study group:

- ≤ 450 msec
- $450 < \text{to} \leq 480$ msec
- $480 < \text{to} \leq 500$ msec
- > 500 msec

The number and percentage of patients having change from baseline QT, QTcB, QTcF values that satisfy the following conditions will be presented by time point and study group:

- ≤ 0 msec
- $> 0 \text{ to} \leq 30$ msec
- $> 30 \text{ to} \leq 60$ msec
- > 60 msec

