**Outcome variables*****Safety:***

The primary outcome variables for this study are related to safety:

- Incidence and severity of adverse events
- Incidence and severity of clinical laboratory abnormalities
- Physical examination findings by the patient
- Incidence and severity of ECG abnormalities
- Mean change from Baseline (Visit 2 of Study MIV-711-201) in vital signs (blood pressure, heart rate, temperature) and oxygen saturation
- Categorical summary of observed vital signs and vital sign changes compared to Baseline (Visit 2 of Study MIV-711-201), by patient

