## 7 ENDPOINT AND METHODS OF ASSESSMENT

### 7.1 Primary Endpoint (Study Population A)

The primary objective is to study the safety and tolerability of MIV-711 in OA patients who have received treatment for up to 52 (26+26) weeks.

Safety endpoints:

- Incidence and severity of AEs
- Incidence and severity of clinical laboratory abnormalities
- Physical examination findings by patient
- Incidence and severity of ECG abnormalities
- Mean change from Baseline (Visit 2 of Study MIV-711-201) in vital signs (blood pressure, heart rate, temperature) and oxygen saturation
- Categorical summary of observed vital signs and vital sign changes compared to Baseline (Visit 2 of Study MIV-711-201), by patient

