## 9.5 Statistical Methodology

### 9.5.1 Primary Endpoint (Study Population A)

The primary outcome will be to study the safety and tolerability of 200 mg MIV-711 q.d. over 52 (26+26) weeks in patients with symptomatic and radiographic knee OA.

Safety endpoints:

- Incidence and severity of AEs
- Incidence and severity of clinical laboratory abnormalities
- Physical examination findings by patient
- Incidence and severity of ECG abnormalities
- Mean change from Baseline (Visit 2 of Study MIV-711-201) in vital signs (blood pressure, heart rate, temperature) and oxygen saturation
- Categorical summary of observed vital signs and vital sign changes compared to Baseline (Visit 2 of Study MIV-711-201), by patient

Safety and tolerability will be assessed descriptively in summary tables presented over time. All data presentations addressing the primary outcome will use Study Population A.

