### **9.5.4 Safety**

The primary purpose and endpoint of the present study is safety and tolerability as described above. There will be no formal statistical hypothesis testing for safety data in this study, therefore only summary statistics will be provided. Safety summaries will be presented by scheduled assessment for the SAF. Summary statistics (number of observations, mean, SD, median, minimum and maximum values) will be presented for continuous variables, and number and percentages (n, %) will be presented for categorical variables. Where applicable, changes from Baseline will also be summarised over time.

Treatment-emergent adverse events will be summarised by preferred term and system organ class and classified according to the latest version of coded Medical Dictionary for Regulatory Activities (MedDRA). The number and percentage of TEAEs will be summarised by system organ class and preferred term in the SAF. Treatment-emergent adverse events will be further summarised with respect to severity and relationship to IMP. Treatment-emergent adverse events related to IMP, leading to withdrawal, serious TEAEs, and deaths will be summarised.

Clinical laboratory tests (haematology, serum chemistry), ECG, and vital signs will be summarised for the SAF at each scheduled assessment. Potentially clinically important findings will also be summarised and listed.

The number of patients taking rescue medication (see definition in Section 6.6.1), the amount of rescue medication taken and the reason for use will be tabulated and summarised descriptively.

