Table 14.3.1.6	Number and Percentage of Patients with Treatment Emergent Adverse Events by Frequency, Preferred Term, and Group
Table 14.3.2.1	Clinical Laboratory Chemistry Summary of Observed Values, SAF Population
Table 14.3.2.2	Clinical Laboratory Hematology Summary of Observed Values, SAF Population
Table 14.3.2.3	Clinical Laboratory Chemistry – Shift From Baseline to Maximum Value, SAF Population
Table 14.3.2.4	Clinical Laboratory Chemistry – Shift From Baseline to Minimum Value, SAF Population
Table 14.3.2.5	Clinical Laboratory Hematology – Shift From Baseline to Maximum Value, SAF Population
Table 14.3.2.6	Clinical Laboratory Hematology – Shift From Baseline to Minimum Value, SAF Population
Table 14.3.3	Vital Signs Blood Pressure and Heart Rate Summary of Observed and Change from Baseline Values, SAF Population
Table 14.3.4.1	12 Lead ECG – Summary of Observed and Change from Baseline Values SAF Population
Table 14.3.4.2	12-Lead ECG – Categorical Summary of Observed Values, SAF Population
Table 14.3.4.3	12-Lead ECG – Categorical Summary of Change From Baseline, SAF Population

PAREXEL International Statistical Analysis Plan

Medivir
Protocol: MIV-711-202

Final 1.0
16 January 2018

12. Figures

TLF Number	Title
Figure 14.2.1.1	Estimated Mean \pm 95% CI for MRI of Bone Area by Week and Group, ITT Population
Figure 14.2.1.2	Estimated Mean \pm 95% CI for MRI of Cartilage Thickness by Week and Group, ITT Population
Figure 14.2.1.3	Estimated Mean \pm 95% CI for MRI of Total BML Volume by Week and Group, ITT Population
Figure 14.2.1.4	Estimated change from Visit 2 MIV-711-201 \pm 95% for MRI of Bone Area by Week and Group, ITT Population
Figure 14.2.1.5	Estimated change from Visit 2 MIV-711-201 \pm 95% for Cartilage Thickness by by Week and Group, ITT Population
Figure 14.2.1.6	Estimated change from Visit 2 MIV-711-201 \pm 95% for MRI of Total BML Volume by Week and Group, ITT Population
Figure 14.2.1.7	Estimated change from Visit 2 MIV-711-201 \pm 95% for MRI of Bone Area by Week and Group, PPS Population
Figure 14.2.1.8	Estimated change from Visit 2 MIV-711-201 \pm 95% for Cartilage Thickness by Week and Group, PPS Population
Figure 14.2.1.9	Estimated change from Visit 2 MIV-711-201 \pm 95% for MRI of Total BML Volume by Week and Group, PPS Population
Figure 14.2.3.1	Estimated Mean \pm 95% CI for NRS Items by Week and Group, ITT Population

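### The SAP only partly delivers the two vital-sign primary endpoints: temperature and oxygen saturation get no change from baseline and no summary, and there is no categorical vital-sign table

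*SAP*

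**What the plan says.** The protocol synopsis states that "The primary outcome variables for this study are related to safety". Protocol 7.1 lists six safety endpoints for Study Population A, and 9.5.1 repeats the list. Two concern vital signs. The first is a continuous measure: "Mean change from Baseline (Visit 2 of Study MIV-711-201) in vital signs (blood pressure, heart rate, temperature) and oxygen saturation". The second stands next to it in both lists, uses the same parent-study baseline and asks for a tabulation instead: "Categorical summary of observed vital signs and vital sign changes compared to Baseline (Visit 2 of Study MIV-711-201), by patient".

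Protocol 9.5.1 also gives the form of reporting: "Safety and tolerability will be assessed descriptively in summary tables presented over time". Protocol 9.5.4 adds that "ECG, and vital signs will be summarised for the SAF at each scheduled assessment", and excludes no parameter.

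SAP 4.4.4 confirms that all four kinds of measurement are taken at every clinic visit. SAP 9.3 has the observed values of all of them listed, but derives change from baseline for blood pressure and heart rate only. It then limits the summary in the same way: "For systolic and diastolic blood pressure and heart rate, the observed values and change from baseline data will be summarized by group". The one vital-sign table in SAP section 11 is Table 14.3.3, titled "Vital Signs Blood Pressure and Heart Rate Summary of Observed and Change from Baseline Values, SAF Population".

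**The concern.** In a study without hypothesis tests, the descriptive tables are the primary analysis. If a parameter named in a primary endpoint has no derived change and no summary, that part of the primary result will not appear in the report unless someone adds it later. The same holds for a categorical summary that no output provides. At stake is whether the safety results named in advance are fully reported, and whether a reader can see that the SAP narrowed the list. The SAP does not say that it did.

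**Working it through.** The plan gives no figure to reproduce, so the check sets each promised element against the SAP text, the output index (SAP sections 11 to 13) and the shells (sections 14 and 15).

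**Mean change from baseline (Protocol 7.1, 9.5.1)**

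| Parameter | Observed values listed (Listing 16.2.8.5) | Change derived (SAP 9.3, Listing 16.2.8.6) | Summarised (Table 14.3.3) |
|---|---|---|---|
| Systolic blood pressure | yes | yes | yes |
| Diastolic blood pressure | yes | yes | yes |
| Heart rate | yes | yes | yes |
| Temperature | yes | no | no |
| Oxygen saturation | yes | no | no |

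Counting blood pressure as two parameters, 3 of 5 are summarised and 5 − 3 = 2 are not. The other outputs agree with this reading:

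- The programming note under the Table 14.3.3 shell adds diastolic pressure, heart rate and weight, but neither missing parameter.
- The Listing 16.2.8.6 shell has columns for heart rate and the two pressures only.
- The vital-sign figures, 14.2.7.1 and 14.2.7.2, cover systolic pressure and heart rate.

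**Categorical summary of observed values and changes (Protocol 7.1, 9.5.1)**

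| Output | Vital signs | ECG, for comparison |
|---|---|---|
| Categorical table, observed values | 0 | 1 (Table 14.3.4.2) |
| Categorical table, changes | 0 | 1 (Table 14.3.4.3) |

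The nearest vital-sign output is Listing 16.2.8.7. It shows, patient by patient, assessments judged abnormal and whether they were clinically significant. It contains no counts and no categories of change.

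**Size.** Of the six primary endpoints, one is summarised for 3 of its 5 parameters and one has no table, so 2 of 6 are incompletely delivered.

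**Declared departures.** SAP 4.6 commits to explaining one discrepancy with the protocol, on analysis populations, in the study report. Neither it nor SAP 9.3 mentions the vital-sign endpoints.

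**The case against.** Five points can be made for the SAP.

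1. *The data are reported.* Observed temperature and oximetry are listed for every patient and visit, so change can be recomputed. This stands as far as it goes: a reader might infer that these parameters have no output at all, and that would be wrong. But a listing of raw values is not a mean change.
2. *The categorical endpoint is worded by patient, and Listing 16.2.8.7 is a by-patient categorical output.* SAP 9.5 treats the physical-examination endpoint, also worded by patient, with a listing. So it would be too strong to say that the categorical endpoint goes wholly unreported. Still, the protocol asks for a summary covering both observed values and changes. A listing of abnormal assessments is not a summary and does not address change.
3. *SAP section 6 has a general rule that observed and change values are tabulated by visit and group.* It qualifies the summary of continuous variables with an as-appropriate clause, and it gives way to the specific text of SAP 9.3 and the shells, which name their parameters. Nor does it supply change values that are never derived.
4. *Protocol section 9 lets deviations from planned analyses be described and justified in the final report.* This stands: silence in the SAP does not by itself breach the protocol. Nothing in the SAP, however, commits anyone to that explanation for these endpoints.
5. *The protocol defines no vital-sign categories.* This also stands. The ECG tables rest on thresholds written into SAP 9.4, whereas a vital-sign table would first need its own.

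A reader might also infer that a confirmatory safety claim is at risk. The documents do not support that: Protocol 9.2.1 says the study is not powered for confirmatory analysis, and 9.5.4 rules out hypothesis testing of safety data.

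**Conclusion.** The mismatch is real and should be corrected. Followed as written, the SAP leaves temperature and oxygen saturation without a derived change or a summary, and leaves the categorical endpoint with only a listing of abnormal assessments. That is 2 of 5 mean-change parameters, 0 categorical tables, and 2 of 6 primary endpoints incompletely delivered, with no declared departure. The consequence is limited to the completeness of descriptive safety reporting. No data are lost and no error rate or test is involved.

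The conclusion assumes that the specific wording of SAP 9.3 and the shells governs over the general rule in SAP section 6, and that a by-patient listing without counts is not the categorical summary the protocol names.

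**What to change.** 1. In SAP 9.3, add temperature and oxygen saturation to the change-from-baseline derivation and to the summarised parameters. Extend Table 14.3.3, including its title and programming note, and Listing 16.2.8.6 to match. For Group A both outputs already use the baseline named in the protocol, so no new baseline rule is needed for the primary endpoint.
2. Add categorical tables of observed vital signs and of changes from baseline, by group and time point, laid out like Tables 14.3.4.2 and 14.3.4.3. State the categories in the SAP before analysis, since the protocol gives none. Because the protocol words this endpoint by patient, say whether a table counting patients in each category is how that wording is read.
3. If the categorical tables are not wanted, declare and justify the omission in the study report section on changes to planned analysis, as SAP 4.6 already does for the analysis populations.

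The cost is a small amount of extra programming on data already collected at every clinic visit, plus the work of agreeing categories for each parameter. That second task is a decision for the study team as well as a programming job.

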## 7.7 12-lead Electrocardiograms (ECG)

A 12-lead ECG will be performed at all clinic visits. 12-lead serial ECGs will be recorded at Visit 2 (Enrolment) pre-dosing and after 30 minutes, 1 hour and 2 hours post-dosing ( $\pm 10$  minutes).

On dosing days, ECG should be performed 30 minutes after dosing ( $\pm 10$  minutes).

The 12-lead ECG will be performed after the patient has been resting in a supine position for at least 10 minutes.

All ECGs will be assessed by the investigator, and the data will be recorded in the eCRF. The clinical significance of ECG results will be determined by the investigator after review of the ECG report in relation to the patient's medical history, physical examination findings, and concomitant medications.

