All pre- and post-dose assessments including unscheduled assessments will be included in the data listings. For unscheduled assessments collected pre-dose, the last assessment taken for a time point will be used in the data summaries (summary tables, figures, and statistical analysis); for all post-dose time points, the original assessment for any given time point will be used in the data summaries (summary tables, figures, and statistical analysis).

Descriptive statistics for observed values and derived change from baseline values will be tabulated by visit and study group. Continuous variables will be summarized by study group and visit, as appropriate, using descriptive statistics including: number of observations (n), mean (arithmetic), median, standard deviation (SD), minimum, and maximum. Frequencies and percentages will be used for summarizing discrete (categorical) data by study group and visit, as appropriate. The denominator used when calculating percentages will be the number of patients assessed at a particular combination of study group and study visit, as appropriate.

Safety and efficacy data that are reported as missing will be excluded from all descriptive and non-descriptive data analysis. There will be no imputation of any data. Observations that might be considered spurious (extreme relative to the majority of the data) will not be altered or removed from any presentation of the data, including the calculation of summary statistics (means, medians, etc.), unless approved by the sponsor.

For data listings, all raw data will be reported/displayed exactly as provided. For summaries of quantitative safety data, the minimum and maximum value will be reported exactly as the raw data are reported; measures of central tendency (means, medians) will be reported to one more decimal place than the raw data; measures of variance (SD) will be reported to two more decimal places than the raw data.

Unless stated otherwise there will be no adjustment for multiple comparisons.

PAREXEL International Statistical Analysis Plan

Medivir
Protocol: MIV-711-202

Final 1.0
16 January 2018

In all data presentations ‘Treatment’ will be defined as 200 mg MIV-711. Listings will include all patients and will be sorted by patient number and time point (where applicable). All derived data used in a data summary or statistical analysis will be listed.

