9.2 Clinical Safety Laboratory Tests (Hematology, Chemistry, Urinalysis)

9.2.1 Hematology and Chemistry

A by-patient listing of all observed chemistry and hematology laboratory data will be provided. Laboratory results outside the normal range will be flagged. The abnormal values will be flagged with ‘L’ (low) for values below the lower limit of the laboratory’s normal range or ‘H’ (high) for values above the upper limit of the laboratory’s normal range. Abnormal values will be graded as not clinically significant (NCS) or clinically significant (CS). Clinically significant laboratory results will be included in the AE listings.

The observed values of all safety laboratory assessments for clinical chemistry and hematology will be summarized using descriptive statistics showing the number of

PAREXEL International Statistical Analysis Plan

Medivir
Protocol: MIV-711-202

Final 1.0
16 January 2018

observations (n), mean, median, SD, minimum, and maximum value. Table summaries will be presented by time point.

Baseline values for all clinical chemistry and hematology parameters will be categorized as being below the normal range (Low), within the normal range (Normal), and above the normal range (High). In addition, the minimum and maximum score over visits post baseline will be calculated and categorized into Low, Normal and High. Note that the minimum/maximum are taken over visits post the baseline visit, i.e. visits when the patients are on 200 mg MIV-711. Shift from baseline tables of the minimum category score and the maximum category score will be tabulated displaying frequency counts and percentage of patients in each (low, normal, high)-matrix by study group.

All hematology, chemistry, and coagulation, laboratory parameters noted in Section 4.4.2 of this SAP will be tabulated.

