VISIT 2	n	nn		nn	nn
MIV-711-201	Mean	xx.x		xx.x	xx.x
DAY 1	SD	xx.xx		xx.xx	xx.xx
	Median	xx.x		xx.x	xx.x
	Min	xx		xx	xx
	Max	xx		xx	xx
VISIT 3	n	nn	nn	nn	nn
MIV-711-201	Mean	xx.x	xx.x	xx.x	xx.x
WEEK 2	SD	xx.xx	xx.xx	xx.xx	xx.xx
	Median	xx.x	xx.x	xx.x	xx.x
	Min	xx	xx	xx	xx
	Max	xx	xx	xx	xx
Visit 4	n	nn	nn	nn	nn
MIV- 711-201	Mean	xx.x	xx.x	xx.x	xx.x
WEEK 3	SD	xx.xx	xx.xx	xx.xx	xx.xx
	Median	xx.x	xx.x	xx.x	xx.x
	Min	xx	xx	xx	xx
	Max	xx	xx	xx	xx
Etc...					

Baseline is defined as: Visit 2 in the MIV-711-201 for Group A, Visit 2 in the MIV-711-202 for Group B
QTcB = QT corrected according to Bazett, QTcF = QT corrected according to Fridericia.

PAREXEL International SAP Amendment Shells

Medivir
Protocol: MIV-711-202

Final 1.0
16 January 2018

Medivir
Protocol Number: MIV-711-202

Page X of Y

Table 14.3.4.2
12 Lead ECG - Categorical Summary of Observed Values
SAF Population

Parameter = QT (msec)

Visit	Category (unit)	Group A N = x	Group B N = x
VISIT 1	≤ 450	nn (nn.n%)	nn (nn.n%)
MIV-711-201	450 < to ≤ 480	nn (nn.n%)	nn (nn.n%)
SCREENING	480 < to ≤ 500	nn (nn.n%)	nn (nn.n%)
	>500	nn (nn.n%)	nn (nn.n%)
VISIT 2	≤ 450	nn (nn.n%)	nn (nn.n%)
MIV-711-201	450 < to ≤ 480	nn (nn.n%)	nn (nn.n%)
DAY 1	480 < to ≤ 500	nn (nn.n%)	nn (nn.n%)
	>500	nn (nn.n%)	nn (nn.n%)
VISIT 3	≤ 450	nn (nn.n%)	nn (nn.n%)
MIV-711-201	450 < to ≤ 480	nn (nn.n%)	nn (nn.n%)
WEEK 2	480 < to ≤ 500	nn (nn.n%)	nn (nn.n%)
Etc...	>500	nn (nn.n%)	nn (nn.n%)

Baseline is defined as: Baseline is defined as: Visit 2 in the MIV-711-201 for Group A, Visit 2 in the MIV-711-202 for Group B

QTcB = QT corrected according to Bazett, QTcF = QT corrected according to Fridericia.

Programming note: Table will include: QTcB interval and QTcF interval

PAREXEL International SAP Amendment Shells

Medivir
Protocol: MIV-711-202

Final 1.0
16 January 2018

Medivir
Protocol Number: MIV-711-202

Page X of Y

Table 14.3.4.3
12 Lead ECG - Categorical Summary of Change from Baseline
SAF Population

Parameter = QT (msec)

Visit	Category (unit)	Group A N = x	Group B N = x
VISIT 1	<= 0	nn (nn.n%)	nn (nn.n%)
MIV-711-201	>0 to ≤ 30	nn (nn.n%)	nn (nn.n%)
SCREENING	>30 to ≤ 60	nn (nn.n%)	nn (nn.n%)
	>60	nn (nn.n%)	nn (nn.n%)
VISIT 2	<= 0	nn (nn.n%)	nn (nn.n%)
MIV-711-201	>0 to ≤ 30	nn (nn.n%)	nn (nn.n%)
DAY 1	>30 to ≤ 60	nn (nn.n%)	nn (nn.n%)
	>60	nn (nn.n%)	nn (nn.n%)
Etc...			

Baseline is defined as: Visit 2 in the MIV-711-201 for Group A, Visit 8 in the MIV-711-201 for Group B

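### No planned ECG table counts, once per patient, who ever exceeded a QTc category while on 200 mg MIV-711

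*SAP*

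**What the plan says.** Protocol 7.1 and 9.5.1 include "Incidence and severity of ECG abnormalities" among the primary safety endpoints for Study Population A over 52 weeks. Protocol 9.5.1 calls for descriptive tables over time. Protocol 9.5.4 calls for ECG summaries at each scheduled assessment and adds that potentially clinically important findings will be both summarised and listed.

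SAP 9.4 sets cut-offs of 450, 480 and 500 ms for observed values, with the layout in "QTcF values that satisfy the following conditions will be summarized by time point and study group". It sets cut-offs of 0, 30 and 60 ms for changes: "QTcF values that satisfy the following conditions will be presented by time point and study group". The shells, including "12 Lead ECG - Categorical Summary of Change from Baseline" (Table 14.3.4.3), repeat one block per visit. The list of summary tables has only three ECG tables, 14.3.4.1 to 14.3.4.3.

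SAP section 6 fixes the percentages: "The denominator used when calculating percentages will be the number of patients assessed at a particular combination of study group and study visit". For post-dose time points, the same section lets only the original assessment into the summaries.

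At patient level, SAP 9.4 has the intervals, including QT, QTcB and QTcF ("corrected QT according to Fridericia) and heart rate will be listed for each patient"), and the changes and the qualitative assessment listed.

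For haematology and chemistry, SAP 9.2.1 goes further: "the minimum and maximum score over visits post baseline will be calculated and categorized into Low, Normal and High". It limits this to visits on 200 mg MIV-711.

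**The concern.** An incidence over 52 weeks asks how many patients were ever affected. A by-visit table answers a different question: how many of those assessed on that occasion were affected. The two cannot be converted into each other, because the table does not show whether the same patient stands behind the counts at different visits. In these tables, one patient with a lasting QTc prolongation and several patients with one exceedance each can look identical.

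Three features of the plan add to this.

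- Protocol 5.3 has patients removed for a confirmed QTcF above 500 ms or a confirmed rise above 60 ms. Such a patient leaves the later on-treatment rows and their denominators, so later visits can look clean because the outlier has gone.
- An exceedance seen only on an unscheduled post-dose ECG enters no table.
- Group B's placebo visits in MIV-711-201 stand in the same tables as its visits on drug.

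**Working it through.** The plan gives no rate, sample size or power for this endpoint, so there is no figure to reproduce. The check is what the by-visit counts can and cannot determine.

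**Inputs**

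- MIV-711-201 ECGs (SAP 4.1, footnote C): Visit 2 pre-dose and 0.5, 1 and 2 h post-dose; one ECG 30 minutes post-dose at each later treatment visit, Visits 3 to 8.
- MIV-711-202 ECGs (Protocol 7.7): "12-lead serial ECGs will be recorded at Visit 2 (Enrolment) pre-dosing and after 30 minutes, 1 hour and 2 hours post-dosing"; one ECG at each of Visits 3, 4 and 5.
- Expected enrolment (Protocol 5.4): 50 to 80 patients in both groups together. The split between groups is not given.

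**Scheduled on-drug time points**

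- Group A, MIV-711-201: 3 post-dose at Visit 2 + 6 (Visits 3 to 8) = 9, over 7 visits.
- Group A, MIV-711-202: 3 post-dose at Visit 2 + 3 (Visits 3 to 5) = 6, over 4 visits.
- Group A total: 9 + 6 = 15 time points, 7 + 4 = 11 visits.
- Group B, MIV-711-202 only: 6 time points, 4 visits.

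These leave out two off-drug recordings: the pre-dose ECG at MIV-711-202 Visit 2, taken after the 10 ± 5 day gap in dosing, and the Visit 6 follow-up ECG. Counting them as post-first-dose would give 15 + 2 = 17 in Group A and 6 + 1 = 7 in Group B, where the Visit 2 pre-dose ECG precedes the first dose.

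**Bounds**

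Let n_k be the number above a cut-off at time point k, and N the group size. Then

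max(n_k) ≤ number ever above ≤ min(N, Σ n_k).

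The counts fix the answer if they are all zero or only one is non-zero. With n_k = 1 throughout, the range is 1 to 15 patients in Group A and 1 to 6 in Group B.

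As percentages for Group A, with assumed group sizes:

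| Assumed N | Lower | Upper |
|---|---|---|
| 40 | 1/40 = 2.5% | 15/40 = 37.5% |
| 55 | 1/55 = 1.8% | 15/55 = 27.3% |
| 70 | 1/70 = 1.4% | 15/70 = 21.4% |

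**The same point as rates**

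Assume a rate p above the cut-off at every time point. The proportion ever above is p if the same patients recur, 1 − (1 − p)^K if the K time points are independent, and Kp if nobody recurs.

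| Assumed p | Group | Same patients | Independent | No overlap |
|---|---|---|---|---|
| 1% | A (K = 15) | 1% | 14.0% | 15% |
| 1% | B (K = 6) | 1% | 5.9% | 6% |
| 2% | A (K = 15) | 2% | 26.1% | 30% |
| 2% | B (K = 6) | 2% | 11.4% | 12% |

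**Baseline for the change categories**

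The count above 60 ms depends on the baseline, and the SAP gives two for Group B. SAP section 9 and the footnote of Table 14.3.4.1 use MIV-711-202 Visit 2. The footnotes of Table 14.3.4.3 and Listing 16.2.8.9 use MIV-711-201 Visit 8. These are different recordings: the Visit 8 ECG is 30 minutes after a placebo dose, whereas the last Visit 2 value before MIV-711 is pre-dose. The mean changes and the categorical changes for Group B would therefore rest on different baselines.

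**The case against.** The strongest reply is that nothing is lost. With 50 to 80 patients and listings showing every value by patient, visit and time point, anyone can count who ever passed 500 ms or rose by more than 60 ms, and can tell a lasting outlier from scattered ones. That stands. A reader might infer from the tables that the incidence cannot be obtained at all; Listings 16.2.8.8 and 16.2.8.9 show that it can. But a hand count is not a planned summary, and Protocol 9.5.4 promises that important findings will be summarised as well as listed.

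Second, a reader might infer that the primary endpoint is the incidence of QTc above 500 ms or of a rise above 60 ms. The documents do not say so. The endpoint names ECG abnormalities in general, and the cut-offs come from SAP 9.4 and the removal rule in Protocol 5.3. ECG findings recorded as adverse events are also counted once per patient in the tables of SAP 9.1. That is partial cover only: it depends on the investigator recording an event, and those tables split MIV-711-201 from MIV-711-202, so Group A gets no single 52-week count.

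Third, the Visit 2 block in the shells might be read as proof that the 1-hour recording has no row. It is not. The shells are abbreviated and end in an et cetera, the text says by time point, and the ECG listings have a time-point column. The shells are unclear, no more.

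Fourth, the lower limit of one patient above the cut-off throughout is unlikely for QTcF in MIV-711-202, because a confirmed exceedance leads to removal. That is fair: the limit is arithmetic, not a forecast. It is not excluded, since removal needs confirmation and refers to QTcF, while the tables also cover QT and QTcB.

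Finally, by-visit summaries are what Protocol 9.5.4 asks for. They should stay; the point is what is missing beside them.

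**Conclusion.** The point holds as a gap in the planned tables. No ECG table gives a once-per-patient count of QTc exceedance on 200 mg MIV-711, although incidence of ECG abnormalities is a primary endpoint and the SAP already tabulates on-drug extremes for laboratory data. The by-visit tables leave the ever-affected number open by a factor of up to 15 in Group A and 6 in Group B in the illustration of one patient per time point. The time-point counts follow from the two visit schedules; the percentages rest on assumed group sizes and assumed rates. The study is descriptive and unpowered, so no error rate is affected. What changes is what a reader can conclude about QTc safety from the tables without going through the listings.

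**What to change.** - Add to Tables 14.3.4.2 and 14.3.4.3 a worst on-drug block by group: each patient's maximum QTcF and QTcB, and maximum increase in each, over all recordings after the first 200 mg dose, including the post-dose serial Visit 2 ECGs. Count each patient once, with all treated patients who have at least one such recording as denominator.
- Define the on-drug window, and say whether Group A's pre-dose ECG at MIV-711-202 Visit 2 and the Visit 6 follow-up ECG are in it. Group B's placebo visits stay out.
- State that unscheduled ECGs count in this block, as an exception to the original-assessment rule in SAP section 6.
- Make explicit in the shells that the serial Visit 2 recordings are separate time points.
- Reconcile the Group B ECG baseline between SAP section 9 and the footnotes of Table 14.3.4.3 and Listing 16.2.8.9, and name the recording used.

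The cost is one derived maximum per parameter, a few table rows and corrected footnotes. All the data are already collected.
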